5.3 Treatment and Evaluation Cycles

At the beginning of each treatment cycle (i.e., every 3 weeks) patients will also have safety laboratory studies, physical examination, assessment of KPS, and complete the MDASI questionnaire. During discussion of the patient's progress, adverse events and concomitant medications will be collected by targeted questioning.

Patients who remain on study will have tumor response assessments performed at 8 weeks (± 7 days) after initiation of therapy and then every 8 weeks (± 7 days) thereafter.

In addition to reassessment scans, confirmatory scans should also be obtained not less than 4 weeks following initial documentation of objective response (OR). To be assigned a status of PR or CR, changes in tumor measurements must be confirmed by repeat assessments that should be performed no less than 4 weeks after the criteria for response are first met.

Patients are to return to the clinic every 3 weeks during the first 6 months on trial. If after 6 months, the patient and the investigator may agree to extend the interval for clinic visits to every 9 weeks (3 cycles). The laboratory assessments must still be performed every three weeks but may be done locally. Brain MRI or CT (for patients who cannot receive MRI scans) will be repeated every 8 weeks, with a 10-day window is allowed after the first 6 cycles.

Unscheduled visits: If a brain surgery or biopsy is scheduled during the active study or within 30 days from the end of treatment date, the investigator may obtain tumor tissue with patient's consent.

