5.4 End of Treatment Visit

Following completion of treatment, for patients who discontinue for toxicity or withdrawal, tumor imaging is at the judgment of the investigator, suggested to be no less than every 8-12 weeks in appropriate setting.

If patients come off treatment for progression of disease, intolerance, or patient withdrawal, they will be seen for assessments of efficacy and safety. Patients will have repeat safety labs, a clinical examination, weight and KPS assessments, and concurrent medications.

If tumor assessments have not been done within the prior 4 weeks, these will be obtained within the next 2 weeks after the End of Treatment Visit.

After the end of treatment, each subject will be followed for 30 days for adverse event monitoring and 30 days (or until start of next line of anticancer therapy) for serious adverse event reporting.

Participants removed from protocol therapy for unacceptable adverse events (Section 7) will be followed until resolution or stabilization of the adverse event.

Subjects who discontinue for reasons other than progressive disease will have post-treatment follow-up for disease status until disease progression, initiating a non-study cancer treatment, withdrawing consent or becoming lost to follow-up.

Subjects will be followed for survival every 30 days after stopping treatment with ONC201.

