5.7 Duration of Follow Up

After documented disease progression each subject will be followed by telephone or medical record review for overall survival. When available, subsequent cancer treatment information and disease imaging up to two years after end of treatment visit will be obtained for patients after discontinuing ONC201 treatment.

Participants will be followed up for survival until one of any of the following criteria apply: lost to follow-up, withdrawal of consent, death.

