The primary efficacy endpoint is PFS-6, defined as the proportion of subjects in the analysis population who remain progression-free for at least six months following initiation of study therapy. Response for the primary analysis will be determined by the investigator assessment, and a confirmation assessment is required per RANO. If patients discontinue protocol therapy at or before 6 months without tumor imaging performed, the patient will be treated in the primary endpoint analysis as a treatment failure. Adjustments will not be made for multiple comparisons.

Secondary efficacy endpoints include: (1) ORR defined as the proportion of subjects in the analysis population who have complete response (CR) or partial response (PR) using RANO criteria; (2) duration of response, defined as time from first RANO response to disease progression in subjects who achieve a PR or better; (3) progression-free survival (PFS), defined as the time from initiation of study therapy to the first documented disease progression according to RANO or death due to any cause, whichever occurs first; and (4) overall survival (OS).

Additional supportive analyses of duration of response and PFS will be conducted using RANO criteria, in which a confirmation assessment of disease progression must be obtained at least 4 weeks after the initial disease assessment indicating progressive disease.

Safety will be assessed by quantifying the toxicities and grades experienced by subjects who have received ONC201, including serious adverse events (SAEs). Other safety endpoints include laboratory safety assessments, KPS status, and vital signs.

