13.3 Statistical Methods for Efficacy Analyses

Efficacy analyses will be performed separately for each arm. Subgroup analyses of the primary tumor location within the brain (e.g. thalamus) and the H3 K27M mutation will be performed across all cohorts. For PFS and OS endpoints, Kaplan-Meier (KM) curves and median estimates from the KM curves will be provided as appropriate. Subjects without efficacy evaluation data or without survival data will be censored at Day 1, as appropriate. Participants without measurable disease will not be included in the analysis of ORR.

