#### 3. Analyses

All analyses will be presented by Arm and for All Patients. Otherwise, specified patient disposition, study drug usage, prior/concomitant/post-ONC201 medications, demographic and baseline characteristics, adverse events, and laboratories will use methods and summaries defined in the ISS SAP.

Laboratory boxplots will be presented for all tests with at least 60 patients having numeric baseline results: one plot per test, time on the x-axis, value on the y-axis. The plots will not be broken out by arm (i.e. only the All Patients group). Only Baseline and Cycles 2-12 will be presented. For Cycles 2-12, nominal visits will be used; if multiple values are associated with a visit, the highest value will be used for chemistry tests and lowest value will be used for hematology tests.

The following efficacy analyses will be performed: best overall response, overall response rate, disease control rate, duration of response, progression-free survival, and overall survival. All analyses will be

based on the investigator-assessed overall RANO response. Discontinuation of treatment due to progressive disease will also be considered. All analyses, aside from overall survival, will be censored at the earlier of: (1) last disease assessment or (2) initiation of other anticancer therapy.

Cycle 1, 2 hour ONC201 plasma concentrations will be summarized descriptively.

Collected data contributing to presented tables and figures will be listed.

Other analyses specified in the protocol will either not be completed, or will be defined outside the scope of this plan.

Following is a complete list of the tables, figures, and listings to be prepared (with clarifying notes in parentheses).

Number	Description
Table 1.1	Patient Disposition
Table 1.2	Demographics and Baseline Characteristics
Table 1.3	Study Drug Usage
Table 1.4.1	Prior Medications
Table 1.4.2	Concomitant Medications
Table 1.4.3	Post-ONC201 Medications
Table/Figure 2.1	Progression-free Survival
Table/Figure 2.2	Overall Survival
Table 2.3	Response Rate (includes ORR, BOR, and DCR)
Table/Figure 2.4	Duration of Response
Table 3.x.1*	Treatment-emergent Adverse Events (TEAE)
Table 3.x.2*	TEAE Grade 3 and Above
Table 3.x.3*	Serious TEAE
Table 3.x.4*	TEAE Leading to Death
Table 3.x.5*	TEAE Leading to Study Drug Discontinuation, Reduction, or Interruption
Table 3.x.6*	Study Drug Related TEAE
Table 3.x.7*	Study Drug Related TEAE Grade 3 and Above
Table 3.x.8*	Study Drug Related Serious TEAE

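### The SAP's censoring rule lets the censoring date for PFS and duration of response depend on whether a scan was recorded after other therapy began, and so counts unscanned time as event-free

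*SAP*

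**What the plan says.** SAP section 3 states one rule for all efficacy outputs other than overall survival: they "will be censored at the earlier of: (1) last disease assessment or (2) initiation of other anticancer therapy". The outputs that depend on a censoring time are Table/Figure 2.1 (PFS) and Table/Figure 2.4 (duration of response).

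The protocol does not fill the gap. Section 13.1 gives PFS as "defined as the time from initiation of study therapy to the first documented disease progression according to RANO or death due to any cause" and does not mention new therapy. Section 13.3 adds only that "Subjects without efficacy evaluation data or without survival data will be censored at Day 1, as appropriate".

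On imaging, Protocol 5.3 schedules "tumor response assessments performed at 8 weeks (± 7 days) after initiation of therapy and then every 8 weeks (± 7 days) thereafter", and later a scan "with a 10-day window is allowed after the first 6 cycles". Protocol 5.4 requires a tumor assessment within two weeks after the End of Treatment Visit if none was done in the previous four weeks. After discontinuation for toxicity or withdrawal, "tumor imaging is at the judgment of the investigator, suggested to be no less than every 8-12 weeks". Disease follow-up of patients who stop without progression ends when non-study treatment starts. Under Protocol 5.7, and only when available, "subsequent cancer treatment information and disease imaging up to two years after end of treatment visit will be obtained".

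**The concern.** The rule is the minimum of two dates. For a patient without an event, the therapy start date can be the earlier one only if an assessment was recorded after therapy started. The presence of that later scan therefore decides between two censoring dates, although it says nothing about disease status on ONC201 alone. Post-switch scans are not mandated, so they will exist for some patients and not for others.

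When the later date applies, the patient stays in the risk set from the last clean scan to the switch without having been scanned in that time. A patient who reaches the switch has, by construction, no recorded event, so the added time is event-free. This raises the Kaplan-Meier curve relative to censoring at the last scan. The arms are read singly against an external rate of about 10%, so no control arm shares the shift.

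**Working it through.** **1. The rule on worked dates.** The plan prints no figure that depends on this rule, so there is none to reproduce. Take clean scans at days 56 and 112, no event, and a switch on day W. The comparison is with censoring at the last assessment on or before W.

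| Switch day W | SAP rule, no later scan | SAP rule, scan at day 168 | Last scan on or before W | Days credited |
|---|---|---|---|---|
| 120 | 112 | min(168, 120) = 120 | 112 | 8 |
| 140 | 112 | min(168, 140) = 140 | 112 | 28 |
| 160 | 112 | min(168, 160) = 160 | 112 | 48 |

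While scans continue on schedule, the credit is limited by one scan interval. That is up to 55 days nominally, and just under 56 + 7 + 7 = 70 days at the limits of the ±7-day window. It is just under 56 + 10 + 10 = 76 days if the later window means ±10. Off treatment the interval can be longer, because imaging is then discretionary.

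**2. What can happen in the credited time.** Assume exponential PFS at the protocol's own rates (13.1). The daily rate is λ = −ln(PFS-6)/182.6, which is 0.01261 at PFS-6 = 0.10 and 0.00659 at 0.30. The chance of progression in g unscanned days is 1 − exp(−λg).

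| g | PFS-6 = 0.10 | PFS-6 = 0.30 |
|---|---|---|
| 28 days | 30% | 17% |
| 56 days | 51% | 31% |

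**3. Effect on the curve.** The two rules were applied to the same simulated patients, with true PFS-6 of 0.10 and 0.30 and scan dates varying by ±7 days. The switching, stopping, later-scan and clinical-detection rates are assumptions and do not come from the documents. Each figure is the rise in six-month Kaplan-Meier PFS, SAP rule minus last-pre-switch-scan rule, when every switcher has a later scan.

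| Setting | Share | Rise (points) |
|---|---|---|
| Scans on schedule until the switch; switching unrelated to progression; 0-30% of progressions found clinically | 20-40% switch | 0.7 to 2.6 |
| Same, but the switch falls between progression and its detection | 20-40% switch | 1.1 to 4.4 |
| Stop on days 14-168, switch 7-70 days later, no scan in between; 20% of progressions found clinically | 20-40% stop without PD | 2.4 to 7.4 |
| As the third row, plus the end-of-treatment scan and clinical detection until the switch | 20-40% stop without PD | 1.3 to 4.4 |
| As the fourth row | 5-10% stop without PD | 0.2 to 0.9 |

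Adding off-treatment imaging every 8-12 weeks in a separate run gave 1.1 to 3.4 points, and 0.1 to 0.7 when 5-10% stop. The rise shrinks as fewer switchers have a later scan. It is near zero if all events fall exactly on nominal scan days and every switch comes within one scan interval of the last scan.

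**4. What these figures measure.** They are differences between two rules, not distances from true PFS. Progression is dated at the scan that finds it, so even with no switching the curve at six months reflects the day-168 scan: exp(−0.01261 × 168) = 0.120 at PFS-6 = 0.10. With 20% switching unrelated to progression and no clinical detection, the SAP rule gave 0.120 and the last-scan rule 0.114. When 40% switched after undetected progression, the two rules gave 0.247 and 0.203, both far above 0.120, and the SAP rule was further off.

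**The case against.** The strongest reply is that few patients can be affected. Progression recorded before the switch is already an event, and the SAP also considers discontinuation for progressive disease. Protocol 11.3.3 counts clinical deterioration as progression. What remains is patients who stop without progression, switch, and are then reassessed. Protocol 5.7 opens with patients who have already progressed, and nothing says that images obtained under it receive an investigator RANO reading. All of this stands, and it limits the size. It does not change how the sentence operates when a later assessment is recorded, and the end-of-treatment scan alone can fall after a switch.

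It can also be said that the authors meant the last assessment before other therapy. A reader might answer that the second clause would then never operate, so the literal reading must be the intended one. That goes too far. The same sentence governs best response, response rate and disease control rate, where the start of new therapy can serve as a data cut-off. The sentence is at least ambiguous. The integrated efficacy SAP cited in SAP section 1 may settle it, but it was not available and the censoring sentence does not defer to it.

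Two stronger readings are tempting and are not supported. One is that the primary endpoint is biased. Protocol 13.1 defines PFS-6 as a proportion and counts discontinuation at or before six months without imaging as failure, and the SAP lists no PFS-6 output. The other is that the shift could be as large as 7 points. That requires 40% of all patients to stop without progression, all of them to have a later scan, and the end-of-treatment scan in Protocol 5.4 to be ignored.

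**Conclusion.** The point holds on the text. For PFS and duration of response, the rule makes the censoring date depend on post-switch imaging and credits unscanned time as event-free. Relative to censoring at the last pre-switch scan, the direction is upward in every setting examined.

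The size is modest. Six-month Kaplan-Meier PFS rises by about 0.2 to 1 point if 5-10% of patients stop without progression, and by about 1 to 4 points if 20-40% do and all have a later scan. These figures rest on assumed rates of stopping, switching, later imaging and clinical detection, with exponential progression. Duration of response was not simulated; the same logic applies there, in the smaller group of responders. The protocol's binary PFS-6 test is untouched. The sentence should be corrected because the correction is simple and removes an arbitrary dependence, not because a conclusion is likely to turn on it.

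**What to change.** For PFS and duration of response, replace the censoring sentence in SAP section 3 with:

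> Patients with no progression or death before initiation of other anticancer therapy will be censored at the last disease assessment on or before that initiation (or at the last disease assessment if none was started; Day 1 if there is no post-baseline assessment). Assessments, progressions and deaths after initiation of other therapy are not used in this analysis.

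The last sentence is needed because death is a PFS event in Protocol 13.1; without it, deaths after the switch could be counted. The Day 1 clause follows Protocol 13.3. For best response, response rate and disease control rate, state separately that assessments after the start of other therapy are excluded.

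The cost is one SAP sentence and one derivation line. PFS and duration of response may look slightly shorter. The change removes the dependence on post-switch scans. It does not remove the informative censoring that arises when patients switch because of undetected progression, so the number censored for other therapy should be shown by arm beside both outputs.

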1.1 Study Design

This is a Phase II multi-center clinical trial with six arms and appropriate stopping rules for poor efficacy.

All subjects in Arm A will receive oral ONC201 every 3 weeks and all subjects in Arm B, C, D, E, and F will receive oral ONC201 every 1 week.

Arm A, B, D, and F will enroll 16-30 evaluable patients each. Arm C will enroll 6 patients who have sufficient resected tumor tissue for correlative studies. Arm E will enroll 12 patients who have sufficient resected tumor tissue for correlative studies. All subjects in Arm C and E will have surgical resection of their tumor 1 day after the second (or more) dose of ONC201.

All subjects will remain on study treatment until progressive disease, unacceptable toxicity, or withdrawal of consent.

All patients will undergo clinical evaluation after each cycle (3 weeks). Neuroimaging studies (contrast-enhanced brain MRI or CT for patients unable to undergo MRI) will be performed at baseline, at 8 weeks from treatment initiation, and then every 8 weeks thereafter.

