1.2 Primary Objectives

To evaluate the anti-tumor activity of ONC201 among patients with recurrent glioblastoma or recurrent WHO Grade IV gliomas when treated with ONC201 as assessed by the 6-month progression-free survival (PFS6) rate using the Response Assessment in Neuro-Oncology (RANO) criteria, for high-grade glioma (HGG).

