13. STATISTICAL CONSIDERATIONS

13.1 Study Design

Arm A will accrue at least 16 evaluable patients. Arms B, D, and F will accrue 16-30 evaluable patients each. Arms C will accrue 6 evaluable patients who have sufficient resected tumor tissue for correlative studies. Arm E will accrue 12 evaluable patients who have sufficient resected tumor tissue for correlative studies. Patients in Arm C or E who after surgery are found to have insufficient resected tumor tissue for correlative studies will continue on treatment but will not count towards accrual of that arm. Data on these patients will be collected. In order to accrue 6 patients onto Arm C with sufficient tissue for correlatives following surgical resection, a total of 12 patients could be enrolled onto Arm C. In order to accrue 12 patients onto Arm E with sufficient tissue for correlatives following surgical resection, up to 18 patients could be enrolled onto Arm E.

The study duration is expected to be 7 years: 6 years for accrual, and 1 year for follow-up on the last participant enrolled.

Efficacy analyses will be performed separately for each arm. Patients enrolled in arms other than Arm D with a known H3 K27M mutation in their glioma may be included in the analyses of Arm D. Among recurrent glioblastoma patients, large meta-analyses of clinical trials evaluating a wide array of salvage therapeutics (excluding bevacizumab) have consistently reported PFS-6 rates of 9-11% ([Ballman 2007](#); [Lamborn 2008](#); [Wu 2010](#)). If the true PFS-6 rate on the current study for patients receiving ONC201 were 30% or higher, there would be interest in further investigation of this treatment regimen. Therefore, this study will be used to detect a difference of 20% using a one-

sided binomial test. Statistically, the hypothesis that will be tested is:

H0: $p \leq 0.1$ versus H1: $p > 0.3$

where p is the proportion of patients achieving PFS-6. Enrollment of 30 patients will yield 84% power to detect a 20% difference at an alpha level of 0.05 (one-sided exact test).

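### The SAP contains neither the PFS-6 proportion nor the one-sided exact test of 10% versus 30% that the protocol makes its primary analysis

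*SAP*

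**What the plan says.** **Protocol.** Section 1.2 sets the primary objective as anti-tumor activity "as assessed by the 6-month progression-free survival (PFS6) rate". Section 13.1 makes the endpoint binary: "The primary efficacy endpoint is PFS-6, defined as the proportion of subjects in the analysis population who remain progression-free for at least six months" after starting study therapy. The hypotheses are a rate of at most 0.1 against a rate above 0.3, and "Enrollment of 30 patients will yield 84% power to detect a 20% difference at an alpha level of 0.05 (one-sided exact test". Efficacy is analysed separately by arm. Section 13.1 also fixes a failure rule: "If patients discontinue protocol therapy at or before 6 months without tumor imaging performed", then "the patient will be treated in the primary endpoint analysis as a treatment failure". On arm sizes, section 1.1 says "Arm A, B, D, and F will enroll 16-30 evaluable patients each"; section 13.1 gives Arm A only a minimum of 16. For PFS as a time-to-event endpoint, section 13.3 asks for Kaplan-Meier curves and medians. It does not ask for a 6-month rate.

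**SAP.** Section 3 names six efficacy analyses: best overall response, overall response rate, disease control rate, duration of response, PFS and OS. Everything except OS is to be censored at the last disease assessment or the start of other anticancer treatment, whichever comes first. The list of outputs is declared complete. Its only PFS entry is Table/Figure 2.1, with no note of a 6-month proportion or a test. On anything else in the protocol, section 3 says: "Other analyses specified in the protocol will either not be completed, or will be defined outside the scope of this plan".

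**The concern.** The SAP is the document from which the tables will be programmed, and it leaves out the one analysis that answers the primary question. A reader cannot tell whether the 10% versus 30% hypothesis will be tested, where, or by what rule.

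If PFS-6 is added later without care, there are two further risks. The censoring sentence in SAP section 3 covers every analysis except OS, so a PFS-6 row added with no exception would fall under censoring instead of the protocol's failure rule. SAP section 2 also treats missing data as missing, again with no exception for that rule. Second, the trial is open-label. If the endpoint rule, the interval level or the test is chosen after outcomes are known, any claim on the primary hypothesis is weakened. Censoring in a Kaplan-Meier analysis of PFS is not itself an error.

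**Working it through.** **1. Element by element**

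| Element | Protocol 1.2, 13.1 | SAP section 3 and output list |
|---|---|---|
| Quantity | Proportion progression-free for at least 6 months | Not listed |
| Null and alternative | 0.10 and 0.30 | Not listed |
| Test | One-sided exact binomial, alpha 0.05 | Not listed |
| Discontinued by 6 months, no imaging | Failure | No such rule; general censoring sentence |
| Source of method elsewhere | – | ISS SAP cited for non-efficacy summaries only; no pointer for PFS-6 |

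**2. Reproducing the protocol's power**

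Inputs from Protocol 13.1: p0 = 0.10, p1 = 0.30, N = 30, one-sided alpha 0.05. With X ~ Binomial(N, p), the test rejects when X ≥ r, where r is the smallest integer with P(X ≥ r | N, 0.10) ≤ 0.05. Power is P(X ≥ r | N, 0.30).

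- r = 6: P(X ≥ 6 | 30, 0.10) = 0.0732, above 0.05.
- r = 7: P(X ≥ 7 | 30, 0.10) = 0.0258, so r = 7.
- Power: P(X ≥ 7 | 30, 0.30) = 0.8405.

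This matches the stated 84%, so the protocol's test is well defined.

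**3. The rule over the planned 16–30 patients**

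| N | Reject at | Exact alpha | Power at 0.30 |
|---|---|---|---|
| 16 | ≥5 | 0.0170 | 55.0% |
| 20 | ≥5 | 0.0432 | 76.2% |
| 21 | ≥6 | 0.0144 | 63.7% |
| 27 | ≥6 | 0.0471 | 86.4% |
| 28 | ≥7 | 0.0179 | 78.0% |
| 30 | ≥7 | 0.0258 | 84.0% |

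The cut-off is 5 for N = 16–20, 6 for N = 21–27 and 7 for N = 28–30, so it has to be set for the N actually reached. One patient decides the result at N = 30: 6/30 gives p = 0.0732 and 7/30 gives p = 0.0258. The rule for classifying patients with missing imaging therefore matters.

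**4. Which interval goes with the test**

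Clopper-Pearson limits at 7/30 (23.3%, p = 0.0258):

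- two-sided 90%: 11.5% to 39.4%, which excludes 10%;
- two-sided 95%: 9.9% to 42.3%, which includes 10%.

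A 95% interval would appear to contradict a significant one-sided 5% test.

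**5. Why a Kaplan-Meier 6-month rate is not a substitute**

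Assumed data, 10 patients: event at month 2, one censored at month 4, event at month 5, seven progression-free beyond month 6.

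- Kaplan-Meier at 6 months: (9/10) × (7/8) = 0.7875.
- Protocol proportion: 7/10 = 0.70 if the month-4 patient discontinued and is taken as lacking the required imaging.
- Protocol proportion: 8/10 = 0.80 if that patient instead began other therapy, was imaged progression-free beyond six months and is counted so. Section 13.1 has no rule for new therapy. Section 5.7 allows for such scans, subject to availability: "disease imaging up to two years after end of treatment visit will be obtained for patients after discontinuing ONC201 treatment".

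The Kaplan-Meier value lies between the two, so the direction of the difference cannot be fixed from the documents.

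**The case against.** The strongest reply is that the test is not lost. The SAP calls itself abbreviated, and its introduction refers to an ISE SAP where approaches are the same. Section 3 calls only on the ISS SAP, so the ISE reference may have been meant for efficacy methods. The protocol already fixes the endpoint, null rate, sidedness, alpha, exact test and failure rule, so a one-sentence cross-reference might be enough. This limits the finding to what this SAP specifies. It does not remove it: no sentence sends PFS-6 to the ISE SAP, and section 3 expressly allows unlisted protocol analyses to go undone.

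Other points have partial force. Applying the censoring sentence to a PFS-6 row is conditional, because no such row exists. In the illustration, the 70% branch assumes that a patient last scanned at month 4 counts as lacking imaging. The 80% branch relies on optional imaging, and Protocol 5.4 ends disease-status follow-up at the start of non-study treatment for patients who stopped without progression. Both bear only on an example labelled as assumed. Neither document sets an interval for PFS-6, so the 90% versus 95% comparison concerns the repair and is not an error in the plan.

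On scope, the 9–11% benchmark comes from recurrent glioblastoma, and Arm F's own entry criterion states no grade. However, Protocol 13.2 uses the same null and alternative for Arms B, D and F. One omission is fair to raise: Protocol 13.1 allows patients with a known H3 K27M mutation from other arms into Arm D's analysis, so Arm D's N needs a rule.

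**Conclusion.** The concern holds. As written, this SAP does not deliver the trial's primary test and must be corrected. What is missing is a rule of at least 7 progression-free patients out of 30 (exact alpha 0.0258, power 84.05%), with cut-offs of 5 or 6 for smaller arms, together with the protocol's failure rule. The power and cut-off figures rest only on the protocol's 0.10, 0.30, one-sided 0.05 and N of 16–30. The Kaplan-Meier comparison rests on assumed data and shows only that the quantities differ; no direction of bias is claimed. Confidence is high that the analysis is unspecified in this SAP. Whether the ISE SAP or another document specifies it cannot be judged from the documents supplied.

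**What to change.** Add one paragraph and one primary table to SAP section 3.

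- For each arm to which the 10% versus 30% hypothesis applies (A, B, D and F), report n/N progression-free for at least six months in the All Treated set. Add an exact two-sided 90% interval (or a one-sided 95% lower bound) and the one-sided exact binomial p-value against 0.10 for the actual N. Report Arms C and E descriptively.
- State that the failure rule in Protocol 13.1 governs PFS-6, and that the SAP's censoring rule applies only to time-to-event analyses.
- State how a patient who starts other anticancer therapy before six months is classified for PFS-6, since Protocol 13.1 is silent.
- State whether H3 K27M patients from other arms count in Arm D's N.
- Keep Kaplan-Meier PFS as a secondary analysis.

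If the test is defined in another document, cite that document and section. If it has been dropped, say so and claim no test of the primary hypothesis.

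Cost: one paragraph and one table, with no new data.
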